a. Care Partners and Persons with Dementia. Up to 40 Care Partners and their 40 care-recipients with ADRD will participate in this study. The primary focus of this study is on Care Partners, however, we will gather subjective and objective data on participants with ADRD to assess the effect of the intervention on Care Partner affective responses to caregiving and quality of life for both. STELLA participants will be recruited from the existing cohort of patients, and their Care Partners, who are enrolled in the ORCASTRAIT Life Laboratory (OSLL).

There has been no pilot testing of STELLA with non-English speaking care partners, and all materials have been tested in English. Therefore, only English-speaking participants are included in STELLA.

b. Inclusion and exclusion criteria. The research team will assess eligibility of interested parties based on the criteria listed in Table 1. In the event of a screen failure, data collected during screening will be destroyed at the end of the study. The recruitment team will track the number of care partners contacted for the study, the number consented, the number of those that dropped out and the number of those that completed the entire intervention.

Table 1: Inclusion/Exclusion Criteria

Participant	Inclusion	Exclusion
Care Recipient	
 Diagnosis of ADRD, moderate to late stages Exhibits 2 or more behaviors listed on RMBPC¹⁶ that are bothersome to the Care Partner and occur 3 or more times/week at study enrollment Family member of Care Partner (this can be a relative, spouse or close kin that is considered family) 	
 Dementia not related to ADRD Unable to leave Care Partner during Partner training Early stage dementia, as defined by MoCA of about 15/30 or higher.

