The STELLA Intervention. STELLA consists of 8 sessions: 4 sessions one-to-one, with the Care Partner and a Guide, and then 4 sessions with one Guide with up to four Care Partners (total small group will include as few as two and as many as 4 Care Partners) (**Table 2**). Each weekly session takes about 1 hour. The first four sessions allow for development of the Care Partner-Guide working relationship. In these sessions, the Care Partners identify behaviors (both the person with dementia's and the Care Partner's) which are upsetting to the family. Care Partners will be taught to use an "ABC" approach to identify activators of behaviors, the behaviors, and consequences of the behaviors. After they identify the ABCs, they will develop a plan to address the behavior and then test it. Based on Care Partner feedback from our pilots, we adapted the prototype intervention so that STELLA uses the ABC plan for both the person with dementia behaviors *and* Care Partner behaviors. After the four one-to-one sessions, Care Partners will meet in small groups with a Guide. Effective communication strategies, engagement in pleasant events, and coping will be addressed (**Table 2**). ⁽⁷⁾ The Guide will facilitate conversation and support between the Care Partners. Care Partners will be provided with each other's contact information. They will be encouraged to contact each other during and after the intervention. Due to schedule conflicts, there may be an up to two-week gap between Sessions 4 and 5.

Each Care Partner will have their own STELLA workbook to document their plans and progress (see "The STELLA Collaborative Handbook"). The booklet will be given or mailed to them prior to the first STELLA visit. They will have access to information on caring for person with dementia on the STELLA password-protected website which is under production. STELLA allows for some flexibility in scheduling if Care Partners have to re-schedule. Care Partners will be advised that the one hour sessions may be tiring and that they may end a session early if needed. In addition, Care Partners will need to find an activity for their care-recipients while they are engaged in the training session so they can focus on the material and protect their care-recipients' dignity. Some of the conversations will include discussions about challenging behaviors, which if overheard by the care recipient, may be upsetting.

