Surveys and subjective assessments will be administered in person via video conferencing or delivered to Care Partners email via a secure system.

Care Partners will be assigned a study ID number which will be used to identify all documents. The key to study ID numbers will be kept in a secure file on a secure OHSU computer.

After the intervention and the second assessment, Care Partners will be asked to participate in a focus group. No less than 3 and no more than 10 Care Partners will participate in each focus group. Focus group participation will be assigned sequentially (e.g., Care Partners 1 through 6 will be in the first focus group) unless Care Partner availability prevents otherwise. The focus groups will be moderated by the PI or a designated team member.

Care Partners who are unable to complete all 8 training sessions will remain in the study and we may collect the data noted in Table 4. These Care Partners may join a focus group if they choose. Care Partners who do not complete any trainings, or are unwilling or unable to adequately follow study instructions and participate in study procedures, will be withdrawn from the study. We will retain and analyze any data from their participation. They may also be asked to complete the assessments, despite not completing all of the trainings.

For some participants, internet connectivity may be problematic. Every effort will be made to help Care Partner maintain a good connection for each visit. A research team member will test their ability to connect and the quality of their connection prior to Session 1 and later visits if needed. In some cases,

at PI discretion, computer (e.g., Chromebook) may be loaned to the research participant for use in the study if available. If, after multiple efforts, a Care Partner cannot maintain a reliable connection for a telehealth visit, they will be excused from the study. They will be allowed to keep the STELLA Handbook.

Guides will be trained by the PI using the Guide Handbook. The PI or other study staff will review their videos for fidelity, using the Consultant Adherence Checklist. During STELLA, videos will be reviewed by the study team for fidelity and team discussion.

Table 3: STELLA Activities

Activity	Description	Due
Preliminary session	Set up and test videoconferencing link	After consent completed
Mercury Baseline (Survey 1)	Baseline assessment (Table 4)	Prior to intervention start

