Intervention (4 weekly sessions)	Meet with for 4 weekly sessions, beginning with Session 1 . (see Table 2)	After Mercury Baseline survey completed
Starlet Survey (Survey 2)	Electronic assessment of depression, burden	1 month after Session 1
Intervention (4 weekly sessions)	Meet with Guide and up to 4 other Care Partners for 4 more weekly sessions (See Table 2)	After session #8
Venus Survey (Survey 3)	Full assessment, including program survey	2 months after Session 1
Post-STELLA Assessment	Complete personalized target problem assessment via Qualtrics or via video or phone call with a Research Assistant	After Venus survey completed
Focus Groups	Optional focus group to provide study team with feedback	After Venus survey completed
Earth Survey (Survey 4)	Full assessment (Table 4)	6 months post-intervention
Earth Survey (Survey 5)	Full assessment (Table 4)	12 months post intervention
ORCASTAIT Surveys	Cost, burden as described in ORCASTRAIT Protocol	Weekly, while in ORCASTRAIT

Phase 1

Measures. Aim 1: Feasibility will be assessed by measuring how many Care Partners who start the program successfully complete it. Care Partners will fill out our telehealth survey that asks them about acceptability.^(23, 24) Acceptability will also be assessed qualitatively using focus groups.⁽²⁵⁾ The focus groups will be conducted via videoconferencing and will be recorded and transcribed for analysis.^(15, 16)

Aim 2: Standard quantitative measures that were used in the earlier pilots^(15, 16) will be used to provide preliminary evidence for efficacy. The quantitative measures are grouped into 5 surveys: Mercury Baseline, Starlet, Venus, Earth (6 months post intervention) and Earth (12 months post intervention). Along with the ORCASTRAIT Living Lab suite of measures (demographics, activity, time with person with dementia, sleep-related behaviors), we assess burden using the RMBPC⁽²⁶⁾ and the 22-item Zarit Burden Interview (ZBI). To provide focus for the intervention, each Care Partner will identify and rate 2-3 specific target problems to address in STELLA. Pre-death grief will be assessed with the Marwit Meuser Caregiver Grief Index, Short Form (MMCGI-SF).⁽²⁷⁾ Care Partner plans for person with dementia placement will be assessed with the

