Aim 2: Efficacy will be assessed by calculating changes in the subjective scores before, during and after the intervention using linear regression models and controlling for age, sex and education. Since this is an exploratory (proof-of-concept) study with a small sample size, we do not expect statistically significant findings, but pre-post change and standard deviation of the change will be used to calculate the sample sizes for the next stage, a RCT (NIH Stage II⁽³²⁾, Phase 1) study.

Objective digital behavioral biomarker data collected from the ORCASTRAIT Living Lab (e.g., daily activity (steps), total sleep time, times together) will be assessed before, during and after the intervention and compared to subjective findings. Simple Spearman correlations will be used to explore the relationship of the objective continuous sensor-derived data to the subjective data, where the continuous objective digital data is collapsed to mean values which will serve as a point estimate prior to, during and after the intervention. We will compare the shift in the distribution of each of the digital behavioral biomarkers from baseline to identify relative changes during and after the intervention. We will compare the objective and subjective findings of the dyad to identify trends that correlate with burden (**Figure 1**)⁽³³⁾.

Aim 2 Anticipated Results and Implications. We anticipate that STELLA will reduce Care Partner burden and grief and improve family quality of life. These improvements in turn will decrease

Care Partner desire to place family members in long-term care. We expect these findings will be supported by both subjective and objective data.

Aim 3: Before Session 5, subjective and objective data (**Table 4**) will be compared to pre, mid- and post-intervention data to identify trends. Qualitative data will be gathered during the focus groups. Participants will be asked what they thought was most helpful about the intervention and what they thought of the format. The objective and subjective results will be used to identify which components of STELLA were most effective and which need to be modified to improve the potency of future iterations.

Aim 3 Anticipated Results and Implications. We expect to see an improvement in the objectives and subjective data, and we expect that we will need to revise the STELLA intervention. We will use information from the focus groups and the accrued data to revise as needed.

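### Sessions 5–8 are delivered in small groups, but neither the planned regression nor the inputs named for sizing the next RCT allow for within-group correlation; if it is positive, precision will be overstated.

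*Combined protocol and SAP*

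**What the plan says.** Section 5, The STELLA Intervention, describes four one-to-one sessions followed by "4 sessions with one Guide with up to four Care Partners", the group being "as few as two and as many as 4 Care Partners". Group members receive each other's contact details, and "They will be encouraged to contact each other during and after the intervention". Table 3 words the group differently: "Meet with Guide and up to 4 other Care Partners for 4 more weekly sessions".

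Section 4a sets the enrolment: "Up to 40 Care Partners and their 40 care-recipients with ADRD will participate in this study". On Guides, Section 5 says "Guides will be trained by the PI using the Guide Handbook" but gives neither their number nor their caseload.

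The Analytic Plan, Phase 1 Aim 2, assesses change in the subjective scores "using linear regression models and controlling for age, sex and education". It describes the study as exploratory, expects no statistically significant findings, and states the onward use of the data: "pre-post change and standard deviation of the change will be used to calculate the sample sizes for the next stage", an RCT. The Phase 2 Aim 2 cost analysis is also a linear regression. Neither analysis mentions group, Guide, an ICC, a random effect or cluster-robust standard errors.

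**The concern.** Care Partners who share a Guide and a group for four sessions, and who are meant to support each other afterwards, share influences on their outcomes. Linking them is a stated purpose of the intervention (Section 1), and the contact that follows is itself surveyed at Venus and Earth. If the mechanism works as intended, change in burden or depression is likely to be positively correlated within a group.

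Ordinary linear regression treats the Care Partners as independent unless told otherwise. With positive correlation, its standard errors for post-group change are too small.

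The RCT matters more. Mean change and its SD are what this study hands forward. A trial of the same group format, sized from those two numbers with no design effect, would have less power than intended. The group effect should not reach the baseline survey, or the Starlet survey one month after Session 1, which falls at about the end of the one-to-one phase. A Guide effect could act from Session 1.

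**Working it through.** The documents contain no power calculation, standard error or RCT sample size to reproduce; 40 is an enrolment cap. The check therefore asks how much the omission could matter.

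**Inputs from the documents.** N is up to 40 Care Partners (Section 4a). Group size m is 2 to 4 (Section 5), which gives 40/4 = 10 to 40/2 = 20 groups.

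**Assumed inputs.** ICC 0.01–0.10. For the RCT: standardised effect d = 0.5, two-sided 0.05, 80% power, 1:1 allocation, no dropout.

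**Step 1: design effect.** DE = 1 + (m − 1) × ICC; the true standard error is √DE times the independent-data one.

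| m | ICC 0.01 | ICC 0.05 | ICC 0.10 |
|---|---|---|---|
| 2 | 1.01 (SE × 1.005) | 1.05 (× 1.025) | 1.10 (× 1.049) |
| 3 | 1.02 (× 1.010) | 1.10 (× 1.049) | 1.20 (× 1.095) |
| 4 | 1.03 (× 1.015) | 1.15 (× 1.072) | 1.30 (× 1.140) |

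Effective sample size, 40/DE, runs from 40/1.01 = 39.6 down to 40/1.30 = 30.8.

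**Step 2: is the pilot SD itself distorted?** The expected sample variance relative to the true one is 1 − (m − 1) × ICC/(N − 1). For m = 4 this is 1 − 0.15/39 = 0.996 at ICC 0.05 and 1 − 0.30/39 = 0.992 at ICC 0.10. The SD is almost unaffected. What is missing is the design effect.

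**Step 3: illustrative RCT.** Under independence, n per arm = 2 × (1.960 + 0.842)²/0.5² = 62.8, rounded up to 63. If only the STELLA arm is grouped and the arms stay equal, n becomes 63 × (1 + DE)/2:

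- m = 2, ICC 0.01: 63 × 1.005 = 63.3, so 64
- m = 4, ICC 0.05: 63 × 1.075 = 67.7, so 68
- m = 4, ICC 0.10: 63 × 1.15 = 72.5, so 73

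If both arms were grouped in fours, 63 × DE gives 65, 73 and 82 at ICC 0.01, 0.05 and 0.10.

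**Step 4: power at an unadjusted 63 per arm, STELLA arm in groups of 4.** Power = Φ(0.5/√((1 + DE)/63) − 1.960).

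- ICC 0.05: 0.5/√(2.15/63) = 2.706, so Φ(0.746) = 77%
- ICC 0.10: 0.5/√(2.30/63) = 2.617, so Φ(0.657) = 74%

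**Step 5: sensitivity to two unsettled inputs.** Table 3's wording allows a Care Partner plus four others, so m = 5: DE = 1 + 4 × 0.05 = 1.20, or 1 + 4 × 0.10 = 1.40. For Guides, if 40 Care Partners were shared among 8, 4 or 2 Guides (5, 10 or 20 each), an assumed Guide ICC of 0.05 gives 1.20, 1.45 or 1.95. Those last figures rest on a caseload and an ICC that the documents do not supply.

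**The case against.** The strongest reply is that no error has yet been made. The plan never states that observations are independent, and the RCT calculation is only announced: no formula, control arm, effect size or power is given. Naming two inputs does not rule out a design effect in a later RCT protocol. Nor do the documents supply any ICC, so a positive value is plausible from the format but not demonstrated. This stands, and it makes the point conditional.

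The reply also holds that the consequence for this study is slight. It is a proof-of-concept study that expects no significant findings and sets no efficacy threshold, and the SD it passes forward is nearly unbiased. This stands too, and puts the weight on the RCT sizing. It does not remove the point, because the model and sizing inputs, followed as written, give optimistic precision under any positive ICC.

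Three stronger readings are tempting and are not supported:

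- A reader might infer that the RCT is undersized. No RCT size exists to judge.
- A reader might infer that each Guide carries a large caseload, so that Guide clustering dominates. The number of Guides is not stated.
- A reader might take a design effect of 1.15–1.30 to mean an arm 15–30% too small. The grouped arm would need 15–30% more; the unadjusted arm falls short by 1 − 1/DE, or 13–23%. With equal arms and only STELLA grouped, the increase per arm is 7.5–15%.

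Finally, group membership might be recoverable from the session recordings or the group logs. But Section 6b has the intervention documents shredded or returned at the end of the intervention, and no group or Guide identifier appears among the measures in Table 4.

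**Conclusion.** The point holds in conditional form. The design creates groups whose members may have correlated outcomes, the planned regression has no term for this, and the inputs named for the RCT omit it. If the ICC is positive and no design effect is added, both the post-group standard errors and the RCT sample size will be too small.

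Over an assumed ICC of 0.01–0.10 and groups of 2–4, the effect is small to moderate: negligible for pairs at the low end, and a true standard error 14% larger for groups of 4 at the high end. For the assumed RCT this means up to 10 more per arm (63 to 73) when only the STELLA arm is grouped, or power of 74–77% instead of 80% for groups of 4 at ICC 0.05–0.10. Guide clustering could add to this by an amount the documents do not allow one to compute. The change is worth making because sizing the RCT is the stated use of these data, but nothing here invalidates the pilot.

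**What to change.** 1. Keep a group ID and a Guide ID for every Care Partner in the analysis file, recorded before the intervention documents are shredded or returned.
2. Report Venus and Earth change with cluster-robust standard errors by group, using a small-sample correction because there will be only about 10–20 groups. Treat Care Partners who never joined a group as singletons, since those who miss sessions stay in the study.
3. Add a sensitivity analysis by Guide, covering Starlet as well, if the number of Guides allows; state that number.
4. State in Phase 1 Aim 2 that the RCT will be sized over ICC 0.01–0.10, with the design effect 1 + (m − 1) × ICC applied to the grouped arm, as a partially nested design if the control arm is not grouped. Use the range rather than the pilot's own ICC, which will be imprecise.
5. Reconcile the maximum group size between The STELLA Intervention text and Table 3, since it enters the design effect.

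The cost is two ID fields, a modest addition to the analysis plan and one sizing statement. The price is slightly wider intervals and a somewhat larger planned RCT.

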Care Partner	
 Adult caring for family member with ADRD Lives with care recipient OR spends at least 4 hours/week with care recipient⁽²¹⁾ Age of 18 years or older Speak English Own a computer/device with a reliable internet connection and compatible operating system 	
 Unable to find activity for care recipient during training which would allow Care Partner to work privately, one-on-one during training Completed similar telehealth intervention within the last year Hearing and vision problems severe enough to prevent participation Unwilling or unable to adequately follow study instructions and participate in study procedures
Both	Participate in ORCASTRAIT (IRB#20236)	

c. Vulnerable populations. The primary focus of this study is to assess the feasibility, costs, and efficacy of subjective and objective measurements of Care Partner and person with dementia responses to the STELLA intervention. Therefore, in order for this study to be successful, participants with moderate to late stage ADRD will be recruited. Few interventions address the needs of families in these later stages.

We will ask that a legally authorized representative (LAR) and, if appropriate, the person with ADRD, if the person with ADRD is competent to make a decision about participation. If the LAR and/or the person with ADRD are concerned about competency, the LAR will be asked to make the participation decision. No other vulnerable populations such as children, prisoners, or pregnant women will be included in this study. All Care Partners will be 18 or older.

d. Setting. This study will take place at OHSU. Participants will connect (from their homes or another convenient location) to the research team via direct-to-home, telehealth, video-conferencing and over the telephone at the Layton Aging and Alzheimer's Disease Center. Interventionists will meet with

caregivers via videoconferencing on an OHSU computer and HIPAA secure link. The interventionist may complete the visit from his or her home, OHSU office or other convenient private location. They will use a privacy screen so that participants will not see their home or office environments. No others (e.g., family members of interventionists) will be allowed in the room during the intervention. Please see ORCASTRAIT (IRB#20236) protocol for details of living lab.

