Care Partners and their family members with dementia will participate in STELLA for a total of 18 months (Table 3); however, most of the participatory effort will occur in the first two months. In this two-month period, Care Partners will participate in the STELLA intervention and complete surveys listed in Table 4. In the next 16 months, we will ask them to complete on-line surveys per the schedule noted in Table 4. Care Partners will receive an email from the study team asking them to open the Qualtrics or REDCap survey. Once they are in Qualtrics or REDCap, they will receive a welcome message from the PI and study team (see invites and reminder messages). Their family members with dementia will not have any STELLA activities, but we will be analyzing their data during the 18-month period.

All STELLA sessions will occur via videoconferencing and will be video-recorded. The video-

conferencing and recording will occur via the OHSU Telehealth Department's HIPAA-compliant, secure systems. Participants will use their own computers to access the study. However, some Care Partners may need to borrow a device. If this is the case, we will lend them a Chromebook. Chromebooks require an internet connection to function and a Google email (Gmail) account to use the STELLA application. We will advise participants in the consent form that they may use their own Gmail account but there is a risk that some of their personal information may be stored on the Chromebook. Alternatively, we can create a Gmail account for them.

Table 2: STELLA Curriculum

Week	Format	Topic
1	One Guide to one Care Partner	Introduction to dementia and behavior management
2		Addressing behaviors
3		Care Partner care
4		ABCs in action
5*	One Guide with up to 4 Care Partners	Communication and dementia
6		Pleasant events
7		Putting it altogether
8		Moving forward, staying connected

*There may be a 2 week break between weeks 4 and 5 if there are scheduling challenges

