We will provide them with the secure link to the videoconferencing system. The *direct-to-home* STELLA visits will be done using real-time delivery of telehealth interactions over distance using videoconferencing technology. The basic mode of connectivity between the study participants and the research team will be via the OHSU Telehealth Department's identified interface. This technology allows face-to-face, highly secure video connections to remote locations. Using their existing device (PC, Mac, iPad, smartphone, etc.), with both visual and audio capabilities, participants will be connected with the research team. The visits will be recorded using the OHSU server. The recorded visits will can be used (with participant consent) to teach and instruct students and clinicians in how to conduct high-quality telehealth care, thus facilitating dissemination of the approach in Oregon and nationally. We have successfully used this clinical-grade telehealth technology in our previous intervention studies. ^(15, 22) On occasion, Care Partners may not be able to connect to the videoconferencing connection due to low bandwidth. In this case, they may meet with the Guide via phone.

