ZBI ³³	
CESD-10 ³⁴	
MMCGI-SF ³⁵	
Placement plan scale ³⁷	
QoL-AD	
STELLA contact	STELLA care partner contact post intervention
STELLA Experience Survey	16-item + comments on satisfaction, privacy, ease of use
Earth Assessment	
RMBPC ²³	
 • See Baseline for descriptions • Baseline: 
 + STELLA contact survey -Experience Survey
ZBI ³³	
CESD-10 ³⁴	
MMCGI-SF ³⁵	
Placement plan scale ³⁷	

QoL-AD	-Demographic survey
STELLA contact	

Phase 2

Aim 1. Quantify the costs of delivering the STELLA intervention. This will measure the direct costs of delivering the intervention (wage multiplied by time of all personnel supporting the intervention) as well costs of technology and equipment, and any in-kind donations of equipment or time to support the intervention.

Aim 2. Quantify the cost efficacy of STELLA in relation to BPSD frequency and CP reactivity and assess the relationship between costs, BPSD, and care partner burden.

Out-of-pocket costs for participating dyads will be collected using an addition to the weekly online ORCASTRAIT survey. CPs will be queried about personal funds spent on health care services, co-pays, medications, or equipment. CP time dedicated to these care-related activities will also be collected. Implicit costs for families will be calculated by multiplying the average weekly hours of care provided by the CP by the average hourly wage of paid caregivers in Portland, Oregon (approx. \$29).

Analytic Plan.

Phase 1

Aim 1: Feasibility will be assessed by calculating the proportion of enrolled Care Partners who completed the full intervention. Reasons for drop-out and discontinuation will be investigated carefully. Focus group transcriptions will be analyzed for themes of acceptability using narrative analysis.⁽²⁵⁾

Aim 1 Anticipated Results and Implication. We anticipate that the Care Partner will find the STELLA intervention feasible and acceptable. This will provide foundational information for future proposals.

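### Connection failure is handled inconsistently, so Aim 1 completion does not separate phone from video, and those lost to connectivity may be missing from the acceptability and outcome surveys

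*Combined protocol and SAP*

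**What the plan says.** All references are to the combined protocol and SAP.

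- **Eligibility (Section 4b, Table 1, Care Partner).** Inclusion requires: "Own a computer/device with a reliable internet connection and compatible operating system".
- **Delivery mode (Section 5, Phase 1, text around Table 2).** The text before Table 2 states that every session is held and recorded by video. The text after it says "On occasion, Care Partners may not be able to connect to the videoconferencing connection due to low bandwidth", and continues: "In this case, they may meet with the Guide via phone".
- **Device loan (Section 5).** The text before Table 2 says of Care Partners who need to borrow a device: "If this is the case, we will lend them a Chromebook". The paragraph on internet connectivity before Table 3 makes a loan depend on PI discretion and availability.
- **Leaving the study (Section 5, text before Table 3).** Care Partners unable to complete all eight sessions stay in the study, and their Table 4 data may be collected. Those who complete no training, or do not follow procedures, are withdrawn; their data are kept, and they may be asked for assessments. In the next paragraph, a Care Partner whose connection still fails after repeated attempts meets a different rule: "cannot maintain a reliable connection for a telehealth visit, they will be excused from the study". It says only that they keep the handbook.
- **Aim 1 measure.** In Measures, Aim 1: "Feasibility will be assessed by measuring how many Care Partners who start the program successfully complete it". In the Analytic Plan, Phase 1, Aim 1: "Feasibility will be assessed by calculating the proportion of enrolled Care Partners who completed the full intervention". The Analytic Plan adds that reasons for drop-out will be investigated.
- **Sample size (Section 4a).** "Up to 40 Care Partners and their 40 care-recipients with ADRD will participate in this study".

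**The concern.** Aim 1 asks whether an intervention delivered by videoconference is feasible and acceptable. Connection failure is the failure most specific to that mode of delivery, so its handling should be visible in the result.

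Two things are at stake. First, the completion rate is the only quantitative feasibility measure that the Analytic Plan names, and its numerator is not fixed. A Care Partner who did some sessions by phone may or may not have completed the full intervention, and nothing requires the two kinds of completion to be told apart.

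Second, the excusal rule selects on the feature under study. The Experience Survey, which covers satisfaction and ease of use, is part of the Venus Survey, due two months after Session 1. If someone excused for connectivity is not sent it, acceptability is measured mainly in people for whom the technology worked. The same people would be missing from the outcome surveys. The Analytic Plan (Aim 2) takes the pre-post change and its standard deviation from those surveys to size the next trial.

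**Working it through.** The plan gives no expected number of connection failures, no target completion rate and no feasibility threshold, so there is no figure to reproduce. The check sets the passages side by side and then shows how far the rate can move.

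**Passages compared**

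| Question | One place | Another place |
|---|---|---|
| How are sessions delivered? | All by video (before Table 2) | Phone allowed for low bandwidth (after Table 2) |
| What if not all sessions can be done? | Stays in the study | Excused, if the reason is connectivity |
| Who provides the device? | Care Partner must own one (Table 1) | Study will lend (before Table 2); study may lend at PI discretion (before Table 3) |
| What is the completion denominator? | Those who start (Measures, Aim 1) | Those enrolled (Analytic Plan, Aim 1) |
| Do phone sessions count as completed? | Not stated | Not stated |

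The denominators can differ in practice. Table 3 puts the link test after consent and before the first session. A Care Partner excused at that point is enrolled but has not started.

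**Size of the shift in completion**

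Inputs: N = 40, the maximum in Section 4a. Assumed, not from the documents: k Care Partners with lasting connection failure, and m = 4 non-completers for other reasons.

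- (a) Affected Care Partners finish by phone and are counted: (N − m)/N
- (b) Affected Care Partners are excused and kept in the denominator: (N − m − k)/N
- (c) Affected Care Partners are excused before Session 1, with starters as denominator: (N − m − k)/(N − k)

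| k (assumed) | (a) | (b) | (c) |
|---|---|---|---|
| 1 | 36/40 = 90.0% | 35/40 = 87.5% | 35/39 = 89.7% |
| 2 | 36/40 = 90.0% | 34/40 = 85.0% | 34/38 = 89.5% |
| 4 | 36/40 = 90.0% | 32/40 = 80.0% | 32/36 = 88.9% |
| 8 | 36/40 = 90.0% | 28/40 = 70.0% | 28/32 = 87.5% |

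The gap between (a) and (b) is k/N, or 1/40 = 2.5 points per affected Care Partner, whatever m is. For scale, the exact 95% confidence interval for 36/40 is 76.3% to 97.2%.

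**Direction of the effect on acceptability**

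Suppose the other N − k Care Partners all answer the Experience Survey and the k excused do not. The respondents' mean then exceeds the mean over all enrolled by (k/N) × d, where d is the respondents' mean minus the mean that the excused would have given. With k = 4 this is 0.10 × d. The documents give no value for d. A positive d is plausible, because these are the people for whom video delivery failed.

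**The case against.** The strongest reply is that these rules form a ladder: help and testing, a loaned device, phone for an occasional failure, and exit only when repeated attempts fail. A reader might infer that phone, loan and excusal contradict one another outright. The documents do not support that, because the three can coexist. What they lack is any link between the steps: neither the occasional failure nor the repeated attempts has a count, and nothing says whether phone is tried before exit. The ladder also leaves standing the conflicts on video or phone, on staying or being excused, and on device ownership or loan.

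Other readings that go further than the text:

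- *A coordinator chooses the rule.* No passage says so. The loan is at PI discretion, and no decision-maker is named for phone or exit.
- *Excused Care Partners vanish from the denominator.* The Analytic Plan uses enrolled Care Partners, which keeps them in. Coding (c) arises only under the Measures wording and only for failures before Session 1.
- *Their data end.* This is an inference. The text does not say that collection stops, and for withdrawn Care Partners it retains data and allows further assessments. It makes no such provision for those excused for connectivity.
- *Connection failure is hidden.* Drop-out reasons are to be investigated, Section 4b tracks drop-outs and completers, and a missing recording would probably reveal a phone session. These help with exits, but none requires phone completions to be reported.
- *Completion should mean video only.* That is a preference. Phone is an allowed fallback, so completion by any mode is a legitimate measure.

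The number affected may also be small, since reliable internet is an entry criterion and the link is tested before Session 1. That stands, although the same section expects connectivity to be a problem for some participants.

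**Conclusion.** The point holds as an internal inconsistency that affects the reading of Aim 1, and it should be corrected. Followed as written, the plan does not separate phone from video completion, defines the denominator in two ways, and may leave connectivity losses out of the Experience Survey and the outcome data. The last would bias acceptability upward if those lost would have rated the program lower.

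The size cannot be derived from the documents. At 40 enrolled, each affected Care Partner moves completion by 2.5 points between counted by phone and excused; the counts of 1 to 8 affected and 4 other non-completers are assumptions. With one or two affected, the shift is small beside the sampling uncertainty at this sample size. No feasibility threshold exists for the rate to cross, so this is a matter of interpretation and of selective missing data, not of a decision rule being reversed.

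**What to change.** 1. Reconcile Table 1 with the Section 5 text on delivery mode, device loan, staying in the study and excusal. Which management rule applies is for the study team to decide.
2. Use enrolled Care Partners as the single Aim 1 denominator, aligning Measures with the Analytic Plan. Count connectivity exits as not completed and report them as a separate reason.
3. Say whether phone sessions count toward the full intervention. Log the mode of every session, and report completion by video alongside completion by any mode.
4. Continue to offer the emailed surveys, including the Experience Survey, to anyone who stops sessions because of connectivity. This matches the existing provision for Care Partners who cannot finish all eight sessions.

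The cost is protocol wording and one field in the session log. The surveys are already sent by email. The downside is a possibly lower reported completion rate.
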